4.3 Clinical Risks/Benefits of MT1002

Based on the observations from the nonclinical studies and the clinical study noted in the previous sections, MT1002 is expected to be safe for the patients in this study with no anticipated risks.

COVID-19 Related Risk/Benefit Assessment

The COVID-19 pandemic is a globally evolving and dynamic situation. The risk of infection is highly variable and dependent on factors such as country, type of hematological facility, patient characteristics, and continues to vary over time. Treating physicians are aware of the status of the COVID-19 pandemic in their area at a specific time. In order to ensure positive risk/benefit for patients treated in this study, site interest and Investigator assessment of positive local risk/benefit will be established in advance of initiating enrollment.

This document is confidential.

4.4 Study Rationale

Therapies for ACS includes antithrombotic therapy and glycoprotein IIb/IIIa receptor antagonists (GPI) as well as anticoagulant therapy. Additional therapeutic measures that may be indicated include thrombolysis and PCI. The goals of pharmacotherapy in PCI are to reduce morbidity and prevent complications. Heparin has been the mainstay of anticoagulation during PCI in patients with angina and ACS for decades. However, the choice of anticoagulation for PCI remains a hotly debated issue. MT1002 is a novel 32-amino acid synthetic peptide aimed to combine molecular functions of both a direct thrombin inhibitor and a platelet glycoprotein IIb/IIIa receptor antagonist, and other characteristics of an ideal parenteral anticoagulant, i.e., to be immediately effective, easily dosed so as not to require frequent monitoring, free of dose adjustment in renally or hepatically impaired patients, and predictably reversible, indicated for use as an antithrombotic and anticoagulant in patients with ACS and in patients undergoing PCI. This study is to investigate the safety, tolerability, and efficacy of MT1002 in patients undergoing PCI due to ACS with NSTEMI.

Three doses of MT1002 (IV loading + continuous IV infusion) will be sequentially tested. The first dose level is 0.90 mg/kg initial loading dose (bolus intravenous injection) + 1.8 mg/kg/h (infusion) for 4 hours. The second dose level will be based on the results from the first cohort (If the dose is escalated, then the second dose level is 1.2 mg/kg initial loading dose (bolus intravenous injection) + 2.3 mg/kg/h (infusion) for 4 hours; if the dose is de-escalated, then the second dose level is 0.6 mg/kg initial loading dose (bolus intravenous injection) + 1.2 mg/kg/h (infusion) for 4 hours). The third dose will be determined based on the results from the first 2 cohorts. The doses of 0.90 mg/kg+ 1.8 mg/kg/h*4h, and 1.2 mg/kg+2.3 mg/kg/h*4h were tested in the Phase 1 healthy volunteer study and were considered to be safe and well tolerated, with the 1.2 mg/kg+2.3 mg/kg/h*4h dose declared the MTD.

5 STUDY OBJECTIVES AND ENDPOINTS

5.1 Study Objectives

5.1.1 Primary Objective

The primary objective of the study is to determine the safe and well tolerated dose of MT1002 in patients with ACS patients NSTEMI and early PCI.

5.1.2 Secondary Objectives

The secondary objectives of the study are:

- Major adverse cardiovascular events (MACE) within 30 days
- To evaluate the anti-coagulation effect of MT1002 by aPTT and ACT
- To evaluate the anti-platelet effect of MT1002 by PA

5.2 Study Endpoints

5.2.1 Co-Primary Endpoints

The co-primary endpoints of this study are:

- The number of patients with target ACT (200 to 300 seconds [sec]) achieved on MT1002 (with no switch to standard of care) prior to and during PCI and PCI success. PCI success is defined as achievement of < 30% residual diameter stenosis of all treated lesions as assessed by visual inspection or Quantitative Coronary Analysis (QCA), without an in-hospital major adverse cardiac event (death, myocardial infarction [MI], or repeat coronary revascularization of the target lesion)
- AE of interest: bleeding events major (Bleeding Academic Research Consortium [BARC] Type 3–5)

5.2.2 Secondary Endpoints

The secondary endpoints are as follows:

- MACE within 30 days
- AEs of interest: bleeding events, infusion reactions, hypersensitivity reactions, thrombotic events (including stent thrombosis), frequency of abrupt vessel closure (AVC), transient ischemic attack, redo of stent procedure (revascularization), or emergency coronary artery bypass grafting (CABG)
- Minor bleeding events (BARC Type 2)
- General AEs including change from baseline abnormal safety laboratory test results
- ACT, aPTT, PT, TT, FIB, INR
- PA and correlation with PK

- Thrombolysis in myocardial infarction (TIMI) flow
- Percentage of patients who achieve $ACT \geq 200$ sec
- PK of MT1002

5.2.3 Exploratory Endpoints

The exploratory endpoint of this study is: creatine kinase (CK)-MB and troponin I (troponin T can be measured if the local site does not have the troponin I test).

6 INVESTIGATIONAL PLAN

6.1 Description of Overall Study Design and Plan

This is an open-label, sequential-dose escalation/de-escalation trial testing 3 dose levels of MT1002 in patients undergoing PCI due to ACS with NSTEMI. Three doses of MT1002 will be sequentially tested in cohorts of 6 patients each to achieve target ACT.

Pre-specified dose escalation/de-escalation/stopping/continuation rules for the patient cohorts are shown in Table 1 below.

Table 1 Rules for Dose Escalation/De-Escalation/Stopping/Continuation

Continue to next higher dose group if:	Stop study drug infusion temporarily in an individual patient if:	Stop dose group and de-escalate according to protocol if:	Continue the same dose in the next patient cohort (to get more data for initial dose) if:	Stop the study if:
$\leq 2/6$ pat peak ACT > 300	Any ACT > 350 or < 180	$\geq 3/6$ pat peak ACT > 300	$\leq 3/6$ pat peak ACT > 300	> 3/6 pat peak ACT > 350
≥ 3 pts. peak ACT < 200 (Cohort 2)				AND
$\leq 1/6$ pat with BARC 3 to 5	BARC 3 to 5	$\geq 2/6$ pat with BARC 3 to 5	$\leq 1/6$ pat with BARC 3 to 5	> 2/6 pat with BARC 3 to 5
				OR
No SAE due to study drug	Any AE/SAE due to study drug that requires switching patient to standard of care	$\geq 2/6$ SAEs due to study drug	No SAE due to study drug	$\geq 2/6$ SAEs due to study drug
In $\leq 1/6$ pat lab values preventing dose escalation such as LFT up by $\geq 2 \times$ from baseline; platelet count < 50,000; QTcF interval > 500 ms or > 60 ms change from baseline, based on ECGs; or study drug related vital sign changes that require stabilization of hemodynamics with positive inotropes	Lab values preventing dose continuation such as LFT up by $\geq 2 \times$ from baseline; platelet count < 50,000; QTcF interval > 500 ms or > 60 ms change from baseline, based on ECGs; or study drug related vital sign changes that require stabilization of hemodynamics with positive inotropes	In $\geq 2/6$ pat lab value preventing dose escalation such as LFT up by $\geq 2 \times$ from baseline; platelet count < 50,000; QTcF interval > 500 ms or > 60 ms change from baseline, based on ECGs; or study drug related vital sign changes that require stabilization of hemodynamics with positive inotropes	In $\leq 1/6$ pat lab values preventing dose escalation such as LFT up by $\geq 2 \times$ from baseline; platelet count < 50,000; QTcF interval > 500 ms or > 60 ms change from baseline, based on ECGs; or study drug related vital sign changes that require stabilization of hemodynamics with positive inotropes	In $\geq 3/6$ pat lab values preventing dose escalation such as LFT up by $\geq 2 \times$ from baseline; platelet count < 50,000; QTcF interval > 500 ms or > 60 ms change from baseline, based on ECGs; or study drug related vital sign changes that require stabilization of hemodynamics with positive inotropes

Abbreviations: AE, adverse event; ACT, activated clotting time; BARC, Bleeding Academic Research Consortium; ECG, electrocardiogram; LFT, liver function test; pat, patient; QTcF, QT interval corrected by Fridericia's formula; SAE, serious AE.

The decision on dose escalation/de-escalation/stopping or continuation for the patient cohort will be taken by the Study Management Group based on data review of each dose group considering safety, efficacy, drug concentration, and in conjunction with the prespecified criteria.

End of Cohort 1 SMG meeting held on March 23, 2023 recommended to proceed to cohort 3 if patients in cohort 2 shows insufficient anticoagulation effect. Insufficient anticoagulation effect is defined when 3 patients or more treated within cohort 2 dosing regimen experienced at least one ACT<200 seconds and confirmed by Ad Hoc SMG meeting.

All patients will be administered a loading dose of aspirin approximately 325 mg (not exceeding 400mg, if not already on maintenance ASA dose) and will stay on 75-100 mg/day (according to local countries clinical practice guidance) as maintenance therapy. All patients will receive a loading dose of clopidogrel (600 mg) if not already on maintenance dose either before PCI or otherwise at the time of PCI, and then maintain a maintenance dose of 75 mg/day. If the local clinical guidance recommends use of Ticagrelor or Prasugrel, the recommended doses will be: Either before PCI or otherwise at the time of PCI, all patients will receive a loading dose of Ticagrelor 180 mg if not already on a maintenance dose, and then stay on a maintenance dose of 90 mg twice daily. Or either before PCI or otherwise at the time of PCI, all patients will receive a loading dose of Prasugrel 60 mg if not already on a maintenance dose, and then stay on a maintenance dose of 5-10 mg daily.

Patients with symptoms of ACS due to NSTEMI who are being triaged in the Emergency Room/hospital and who are selected for early PCI will be screened for the study. Enrollment should occur be as close to the actual start of PCI as possible. All patients will be given routine care for ACS according to applicable guidelines including analgesics, nitrates, beta-blockers, and potentially additional drugs as needed (anti-arrhythmic drugs, statins, ACE inhibitors/angiotensin II receptor blockers, calcium-channel blockers, proton pump inhibitors, etc).

If a patient meets all the admission criteria and all the eligibility criteria, he/she can be enrolled to receive MT1002 treatment (1 of 3 dose levels) and undergo early PCI (including diagnostic coronary angiography procedure).

Procedure: either radial access/distal radial access PCI or femoral access PCI will be used in this study. It is up to the discretion of the Principal Investigator what type of stent(s), if indicated, will be used.

Follow-up: At completion of PCI, subjects will be continued on IV MT1002 for 4 hours from infusion start. All patients will stay on clopidogrel 75 mg/day. If the local clinical guidance recommends use of Ticagrelor or Prasugrel, the recommended maintenance doses will be: Ticagrelor 90 mg twice daily or Prasugrel 5-10 mg daily and aspirin 75-100 mg/day (according to local countries clinical practice guidance) and be followed up for 30 days. Longer-term follow-on treatment will be done according to local treatment guidelines outside of this protocol.

Rescue: Patients who fail to achieve an ACT target of 200 to 300 sec with MT1002 (within 30 minutes after MT1002 infusion initiation) will be switched to standard of care (unfractionated heparin [UFH] or bivalirudin) and discontinued from the study drug.

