Version 6.0	
Revised dose escalation/de-escalation/stopping /continuation rules based on end of Cohort 1 SMG safety review and recommendation 23Mar2023:
 
 Added “Continue to next higher dose group if 3 or more patients show peak ACT <200 sec in Cohort 2” to avoid inadequate treatment in cohort 2. Modified “Stop study drug infusion in an individual patient only temporarily and eliminate conditions if ACT <180.” The specific dosing adjustment guideline provided, therefore study drug infusion can be resumed to ACT at target level. Modified the criteria in Stop the study if: both more than 3/6 ACT >350 sec and more than 2/6 patients experience bleeding events with BARC 3-5. Both ACT as anti-coagulation level biomarker and actual significant bleeding events with BARC 3-5 are needed to justify study to be stopped due to significant risk of bleeding. 
Proposed new dosing regimen for cohort 3 at 0.75 mg/kg + 1.6 mg/kg/h*4h and dose adjustment guideline for cohort 3 dosing regimen per SMG’s recommendation based on the following findings in Cohort 1 and PK/PD modeling results from Phase I study:
 
 MT1002 was safe and well-tolerated in all 6 patients enrolled in the 0.90 mg/kg+1.8mg/kg/h*4h cohort of the study. None of the patients who received MT1002 experienced serious adverse events, major bleeding events or major adverse cardiovascular events. At 0.90 mg/kg+1.8mg/kg/h*4h dose-level, MT1002 achieved targeted ACT level resulting in successful PCI in all 6 patients. 3 patients had one peak ACT >300 after bolus injection at 5 minute, indicated the bolus dosing at 0.9 mg/kg can be reduced. 0.75 mg/kg is recommended by SMG if 0.6 mg/kg shows inadequate anti-coagulate effect. Only 1 patient had one peak ACT >300 at 30 minutes during infusion period, indicated 	16-Apr-2023
-------------	--	-------------

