	
(according to local countries clinical practice guidance) as maintenance therapy. All patients will receive a loading dose of clopidogrel (600 mg) if not already on maintenance dose either before PCI or otherwise at the time of PCI, and then maintain a maintenance dose of 75 mg/day. If the local clinical guidance recommends use of Ticagrelor or Prasugrel, the recommended doses will be: Either before PCI or otherwise at the time of PCI, all patients will receive a loading dose of Ticagrelor 180 mg if not already on a maintenance dose, and then stay on a maintenance dose of 90 mg twice daily. Or either before PCI or otherwise at the time of PCI, all patients will receive a loading dose of Prasugrel 60 mg if not already on a maintenance dose, and then stay on a maintenance dose of 5-10 mg daily.
 
Patients with symptoms of ACS due to NSTEMI who are being triaged in the Emergency Room/hospital and who are selected for early PCI will be screened for the study. Enrollment should occur once the patient has completed screening and satisfied all the I/E criteria. Initiation of the MT1002 intravenous injection would then only start just before the PCI procedure. All patients will be given routine care for ACS according to applicable guidelines including analgesics, nitrates, beta-blockers, and potentially additional drugs as needed (anti-arrhythmic drugs, statins, angiotensin-converting enzyme inhibitors/angiotensin II receptor blockers, calcium-channel blockers, proton pump inhibitors, etc.).
 
If a patient meets all the admission criteria and all the eligibility criteria, he/she can be enrolled to MT1002 (1 of 3 dose levels) and undergo early PCI (including diagnostic coronary angiography procedure).
 
Procedure: either radial access/distal radial access PCI or femoral access PCI will be used in this study. It is up to the discretion of the Principal Investigator what type of stent(s), if indicated, will be used.
 
Follow-up: At completion of PCI, subjects will be continued on IV MT1002 for 4 hours from infusion start. All patients will stay on clopidogrel 75 mg/day. If the local clinical guidance recommends use of Ticagrelor or Prasugrel, the recommended maintenance doses will be: Ticagrelor 90 mg twice daily or Prasugrel 5-10 mg daily and aspirin 75-100 mg/day (according to local countries clinical practice guidance) and be followed up for 30 days. Longer-term follow-on treatment will be done according to local treatment guidelines outside of this protocol.
 
Rescue: Patients who fail to achieve an ACT target of 200 to 300 sec with MT1002 (within 30 minutes after MT1002 infusion initiation) will be switched to standard of care (unfractionated heparin or bivalirudin) and discontinued from the study drug.

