Clopidogrel: On admission, all patients will receive a loading dose of clopidogrel (600 mg) if not already on a maintenance dose, and then stay on a maintenance dose of 75 mg/day. Patients should continue this ADP/P2Y₁₂ inhibitor for the remainder of the study period (i.e., through 30 days post-dose) or longer per local standard of care, as outlined by the current ACCF/AHA and European Society of Cardiology Guidelines.

Ticagrelor or Prasugrel: if the local clinical guidance recommends use of Ticagrelor or Prasugrel, the recommended doses will be: On admission, all patients will receive a loading dose of Ticagrelor 180 mg if not already on a maintenance dose, and then stay on a maintenance dose of 90 mg twice daily. Or on admission, all patients will receive a loading dose of Prasugrel 60 mg if not already on a maintenance dose, and then stay on a maintenance dose of 5-10 mg daily. Patients should continue this ADP/P2Y₁₂ inhibitor for the remainder of the study period (i.e., through 30 days post-dose) or longer per local standard of care, as outlined by the current ACCF/AHA and European Society of Cardiology Guidelines.

In this study, clopidogrel (or Ticagrelor or Prasugrel) and acetylsalicylic acid are considered non-investigational medicinal products. This means that in the event of an SAE, the Investigator will assess the causal relationship of the SAE to the non-investigational medicinal product.

Bivalirudin: Patients receiving bivalirudin before enrollment into the study for the index MI should not be included in the study. Patients who fail to achieve the ACT target of 200 to 300 sec with MT1002 (within 30 minutes after MT1002 infusion initiation) can be switched to bivalirudin before PCI as a standard of care. Bivalirudin cannot be administered simultaneously with MT1002; MT1002 treatment should be discontinued at least 30 mins before switching to bivalirudin (dosing per local standard of care).

Glycoprotein IIb/IIIa inhibitors: Upstream use of glycoprotein IIb/IIIa inhibitors (i.e., within 24 hours before enrollment) is an exclusion criterion. After enrollment, glycoprotein IIb/IIIa inhibitors may be used as bail out for procedural or angiographic complications or clinical instability (dosing per local standard of care). Glycoprotein IIb/IIIa inhibitors cannot be administered simultaneously with MT1002; MT1002 treatment should be discontinued 30 minutes before switching to glycoprotein IIb/IIIa inhibitors.

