11.6.3 Bleeding Events

Bleeding events are classified as major or minor based on BARC classification. Minor bleeding events are those that meet the criteria for BARC Type 2, and major bleeding events are those meeting the criteria for BARC Types 3 to 5.

BARC definitions are provided in Table 9.

Table 9 Bleeding Academic Research Consortium Definitions

Type	Definition
0	No bleeding
1	Bleeding that is not actionable and does not cause the patient to seek treatment
2	Any clinically overt sign of hemorrhage that “is actionable” and requires diagnostic studies, hospitalization, or treatment by a health care professional
3	
 Overt bleeding plus hemoglobin drop of 3 to < 5 g/dL (provided hemoglobin drop is related to bleed); transfusion with overt bleeding Overt bleeding plus hemoglobin drop < 5 g/dL (provided hemoglobin drop is related to bleed); cardiac tamponade; bleeding requiring surgical intervention for control; bleeding requiring intravenous vasoactive agents Intracranial hemorrhage confirmed by autopsy, imaging, or lumbar puncture; intraocular bleed compromising vision
4	Coronary artery bypass grafting-related bleeding within 48 hours
5	
 Probable fatal bleeding Definite fatal bleeding (overt or autopsy or imaging confirmation)

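### Table 1 labels every individual-patient stop temporary: the switch row is inconsistent with the Rescue text, and the BARC 3 to 5 row says nothing about restart or discontinuation

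*Combined protocol and SAP*

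**What the plan says.** Table 1 in Section 6.1 has five columns. Four are decisions about a cohort or the whole study. The fifth concerns one patient and is headed "Stop study drug infusion temporarily in an individual patient if". Four kinds of trigger stand under it:

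- ACT outside stated limits;
- BARC 3 to 5 bleeding;
- "Any AE/SAE due to study drug that requires switching patient to standard of care";
- laboratory, ECG or vital-sign changes that preclude continuing the dose.

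The synopsis table uses the same heading and the same three non-ACT rows. (The two copies differ on the ACT limits, which is a separate matter.)

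Elsewhere, the Rescue paragraph in Section 6.1 says that patients who miss the ACT target within 30 minutes "will be switched to standard of care (unfractionated heparin [UFH] or bivalirudin) and discontinued from the study drug". The synopsis says the same. Section 8.5.1 adds: "Bivalirudin cannot be administered simultaneously with MT1002; MT1002 treatment should be discontinued at least 30 mins before switching to bivalirudin". It has a parallel rule for unfractionated heparin. Table 9 in Section 11.6.3 shows what BARC 3 to 5 contains. Type 3 includes "Intracranial hemorrhage confirmed by autopsy, imaging, or lumbar puncture; intraocular bleed compromising vision", and Type 5 is fatal bleeding.

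**The concern.** A heading that calls a stop temporary implies that the infusion may resume. That is intelligible for an ACT excursion. It is hard to apply when the trigger is itself a switch to another anticoagulant, and it has no meaning after a fatal bleed. No column in Table 1 ends MT1002 for a single patient, so a site looking there for that instruction will not find it.

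MT1002 is described as both a thrombin inhibitor and a glycoprotein IIb/IIIa inhibitor. If sites read the table differently, exposure after a serious event will differ between patients for reasons unrelated to the assigned dose. The trial exists to find a safe and well tolerated dose from cohorts of about six, so that matters for safety and for interpretation.

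**Working it through.** No sample-size figure bears on this point. The check is a comparison of texts, followed by one illustrative calculation.

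**1. Switch row.** Table 1 makes a switch to standard of care a reason for a temporary stop. The Rescue paragraph pairs the same switch with discontinuation. Section 8.5.1 bars giving bivalirudin or heparin together with MT1002, and requires MT1002 to be discontinued at least 30 minutes (bivalirudin) or 30 minutes (heparin) beforehand. These cannot all be followed under a pause-and-resume reading. Section 8.5.1 also lists the exceptions to its heparin ban. A switch for failure to reach the ACT target is among them, but a switch driven by an adverse event is not, although Table 1 foresees one. One limit applies: the Rescue text is written for ACT failure. Extending it to adverse events rests on the shared term and on the bar to co-administration, not on an explicit rule.

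**2. BARC 3 to 5 row.** Three questions were put to the text.

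- Does anything require discontinuation after one patient's BARC 3 to 5 bleed? No.
- Does anything state when the infusion may restart after a bleed? No. The only pause-and-adjust instruction (Section 8.2 and the synopsis) is driven by ACT and limited to cohort 3.
- Does anything forbid a restart? No. Section 7.3 says that a patient may be withdrawn for unacceptable toxicity or an adverse event, or for a change that makes the patient ineligible for further treatment. That wording is permissive.

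Meanwhile Section 9.2.3 tells sites to continue the infusion to 4 ± 0.5 hours from its start in patients who reached target before PCI. Section 9.2.4 gives 4 hours. Neither addresses a paused patient. The row is therefore a gap, not a contradiction.

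**3. Laboratory row.** In this column the wording concerns values that preclude continuing the dose; the cohort and study columns speak of precluding escalation. Under a temporary heading it is unclear which disposition is meant.

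**4. Effect on endpoints.** The first co-primary endpoint (Section 5.2.1) requires target ACT on MT1002 before and during PCI with no switch to standard of care, plus PCI success. If an event occurs before or during PCI, a patient who is paused and resumed can qualify where a patient who is switched cannot. The second co-primary endpoint concerns major bleeding. A patient stopped for a BARC 3 to 5 bleed has received a dose, so is in the as-treated population (Section 14.2) and is already an event. Section 14.4 takes the greatest severity when the same event recurs. Resuming the infusion does not change that patient's count.

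**5. How often the BARC row might be used.** The documents give no BARC 3 to 5 risk, so per-patient risks p of 1%, 5% and 20% are assumed. The chance of at least one event in n patients is 1 − (1 − p)^n. Cohort 1 (six patients) is complete and the version 6.0 summary reports no major bleeding in it, which leaves up to 18 − 6 = 12.

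| p | n = 6 | n = 12 |
|---|---|---|
| 1% | 1 − 0.99^6 = 5.9% | 1 − 0.99^12 = 11.4% |
| 5% | 1 − 0.95^6 = 26.5% | 1 − 0.95^12 = 46.0% |
| 20% | 1 − 0.80^6 = 73.8% | 1 − 0.80^12 = 93.1% |

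For the re-exposure question these are upper limits at each assumed risk. They include bleeds after the roughly 4-hour infusion, when there is nothing left to pause.

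**The case against.** The strongest reply is that no competent site would restart the drug after a major bleed, and that existing text already limits it. Much of this is fair.

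- On the switch row, Section 8.5.1 prevents MT1002 from running alongside the replacement anticoagulant. That narrows the practical risk, but it does so by overriding the heading, which is the inconsistency at issue.
- On bleeding, Section 7.3 combined with Section 7.2 gives a route out. Active bleeding, any history of intracranial bleeding and platelets below 100,000 are exclusion criteria, so such a patient could be withdrawn as ineligible for further treatment. That route is optional and does not name BARC events.
- On recording, Section 8.4 already captures early termination and its reason, and Section 11.6.1 captures the action taken with study drug.

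Three stronger readings are tempting, and the documents do not support them. A reader might infer that the BARC row also contradicts the discontinuation wording. It does not, because that wording concerns ACT failure. A reader might infer that the protocol directs a restart after a major bleed. No text says so; it only fails to exclude it. A reader might infer that the co-primary bleeding count is distorted. A patient with a BARC 3 to 5 bleed counts once whatever follows.

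It can also be argued from the version 6.0 entry in the summary of changes that the temporary wording was meant for ACT alone. That log describes changes, and the current heading covers every row. The point here rests on the current text.

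**Conclusion.** The point holds in two parts of different strength. The switch row is inconsistent with the Rescue paragraph and Section 8.5.1, on the assumption that a switch to standard of care means the same thing whatever triggers it. The BARC 3 to 5 row is incomplete: it is labelled temporary, includes fatal bleeding, and leaves restart neither regulated nor excluded.

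The consequence is for patient safety and for consistent exposure across about 13 planned sites. It may also extend to classification on the first co-primary endpoint, for events before or during PCI. The number of patients with major bleeding is unaffected. How often the rule will be needed cannot be derived from the documents. Under assumed risks of 1% to 20%, the chance of at least one BARC 3 to 5 event in the 12 patients still to come runs from 11.4% to 93.1%, as an upper limit at each risk. Because this is a stated safety rule that cannot be followed consistently as written, it should be corrected.

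**What to change.** Reconcile the individual-patient column of Table 1 and its synopsis copy with the Rescue paragraphs (Section 6.1 and synopsis), Section 7.3 and Section 8.5.1. Each existing row should state whether the infusion is paused or MT1002 is discontinued for that patient. For any row kept as a pause, the text should say whether and how restart is addressed. Which row belongs where is a clinical decision for the sponsor and the SMG, and none is proposed here.

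In the eCRF, record pause-and-resume separately from discontinuation, with times, in addition to the early-termination and action-taken items already planned.

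The cost is protocol amendment wording and a small eCRF addition, with no extra patients or procedures.
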